6.8.2. Adverse Events

Adverse event (AE) verbatim terms will be provided by the investigators and then will be mapped by Lilly or its designee to corresponding terminology within the Medical Dictionary for Regulatory Activities (MedDRA) Lower Level Term (LLT) dictionary Version 21.0 (or higher). The investigator will use Common Terminology Criteria for Adverse Events (CTCAE) Version 4.0 (NCI 2009) to assign AE severity grades.

Preexisting conditions are defined as AEs that begin but do not resolve prior to the first dose of study drug in each study period. Preexisting conditions will be presented by patient and can be combined with the listing of AE, so that the history of the preexisting conditions/AEs can be traced.

A treatment emergent adverse event (TEAE) is defined as any AE that begins on or after the day of first dose in the reporting study period or any preexisting condition that increases in CTCAE grade on or after the day of first dose in the reporting study period. The MedDRA LLT will be used in the treatment-emergent computation.

The number of patients who experienced a TEAE, or TEAE at least possibly related to study drug, will be summarized. Treatment-emergent adverse events will be summarized by System Organ Class (SOC), by Preferred Term (PT) of decreasing frequency within SOC, and by maximum CTCAE grade and grade categories (any, Grade 3 or higher).

Adverse events leading to dose adjustments, treatment discontinuation, or death will also be summarized.

Dose-limiting toxicities in Phase 1a and DLT-equivalent toxicities in Phase 1b will be summarized by cohort.

6.8.3. Deaths, Other Serious Adverse Events, and Other Notable Adverse Events

All deaths in this study, including the reasons for death, will be listed by treatment. The reasons for death will be summarized, separately for on-therapy, and within 30 days of last dose of study drug.

Serious AEs will be summarized for each treatment by decreasing frequency of PT within SOC. The summary will be provided for events, regardless of study drug causality, and repeated for events deemed by the investigator to be related to study medication.

6.8.4. Clinical Laboratory Evaluation

Listings of laboratory results will be provided. All relevant hematology and chemistry laboratory values will be graded according to CTCAE Version 4. Shift tables showing the change from baseline to the worst grade on study will be presented.

Laboratory analytes below/above quantifiable levels (data in the database recorded as “ $<x$ ” and “ $>x$ ”) will be reported as such in listings, and imputed to the lower or upper limit of quantification in any summaries or analyses.

6.8.5. Vital Signs and Other Physical Findings

Vital signs measurements, including height, weight, temperature, blood pressure, pulse, and ECOG performance status will be listed and summarized.

6.8.6. Electrocardiograms

Local electrocardiograms (ECGs) will be summarized by cycle and overall. The summary by cycle will classify patients as having normal or abnormal. Adverse events that could be associated with abnormal ECGs will be presented, if appropriate.

Quantitative ECG results including PR, QRS, Bazett's corrected QT (QTcB), Fridericia's corrected QT (QTcF), and RR intervals will be provided in patient listings for absolute and change from baseline. In addition, summaries of outlying corrected QT (QTc) intervals (QTc, QTcB, and QTcF) will be provided. Outlying intervals include absolute values >450 for males, >470 for females, >480 and >500 msec, and change from baseline >30 and >60 msec.

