ECG		X	X		X	X	X	X		
ECG collections that are underlined and in bold are mandatory. All other ECG collections are optional.
 
Baseline: Single ECG only
 
Cycle 1 Day 1: collect digital ECGs for QT analysis in triplicate at predose, 2 hrs postdose. If possible, a 24 hr reading should be taken.
 
Day 15: Predose (triplicate) A corresponding PK sample should be collected after the ECG reading.
 
Cycle 2: Single ECGs only (predose on D1 and D15)
 
Cycle 3-n: Single ECG on D1 (predose).
 
Perform additional evaluations in the setting of cardiac symptoms and/or at the discretion of the investigator. Perform locally.
	
Hematology*	X	X		X	X	X	X	X		≤ 3 days prior to start of each cycle, unless more frequent assessment is clinically indicated.	
Coagulation	X									Only collected at baseline, unless more frequent assessment is clinically indicated.	
Clinical chemistry*	X	X		X	X	X	X	X		≤ 3 days prior to start of cycle, unless more frequent assessment is	

Procedure	Baseline	All Remaining Parts on Treatment (Cycle = 28 days)						Post Treatment Follow-Up		Instructions	
	Days Prior to C1D1	Cycle 1 (± 3 Days)			Cycle 2 (± 3 Days)		Cycle 3-n (± 3 Days)	Short-Term ^a (30 ± 7 Days)	Long-Term (Every 90 ± 7 Days)		
		Day			Day		Day				
		≤ 28	1	8	15	1	15	1	Visit 801	Visit 802-8XX	
										clinically indicated.	
Urinalysis*	X	X			X		X	X		≤ 3 days prior to start of cycle, unless more frequent assessment is clinically indicated.	
Urine pregnancy test	X	X			X		X			Applies only to women of childbearing potential. Where required by local law or regulation, perform ≤ 3 day prior to start of every cycle prior to administration of study treatment.	
Patient diary		X		X						Provide patient diary Day 1. Completed daily by patient. Review at each study visit during Cycle 1.	
Survival assessment								X	X	Perform q 3 mo (± 7 days). If an in-person visit is not possible, confirm survival by contacting the patient directly via phone.	
LY3405105		X								Administer orally on Days 1-28 of a 28-day cycle. Patients should be advised to take dose after PK draw on days of PK collection.	

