Table JZFA.2.2. Baseline, On-Study Treatment, and Post Treatment Schedule of Activities for Phase 1b

Procedure	Baseline	All Remaining Parts on Treatment (Cycle = 28 days)					Post Treatment Follow-Up		Instructions
	Days Prior to C1D1	Cycle 1 (± 3 Days)		Cycle 2 (± 3 Days)		Cycle 3-n (± 3 Days)	Short-Term ^a (30 ± 7 Days)	Long-Term (Every 90 ± 7 Days)	
		Day		Day		Day			
		≤ 28	1	15	1	15	1	Visit 801	Visit 802-8XX
Informed consent	X								ICF must be signed before any protocol-specific procedures are performed. Baseline/screening labs or imaging, as part of routine patient care, drawn within the indicated window of C1D1 may be used for both screening/baseline and C1D1 labs.
Physical examination*	X	X	X	X	X	X	X		Perform prior to administration/dispensing of study drug.
Vital signs and weight*	X	X	X	X	X	X	X		Perform prior to administration/dispensing of study drug. Include height (only at baseline), weight, and vital signs (temperature, blood pressure, pulse rate).
Medical history	X								
Inclusion/Exclusion evaluation	X								
Concomitant medication	X	X	X	X	X	X			
AE collection	X	X	X	X	X	X	X	X	CTCAE V4.0. During long-term follow-up, only AEs that are related to study treatment will be followed to resolution.
ECOG performance status or LPS	X	X	X	X	X	X	X		
Radiologic imaging and measurement of palpable or visible lesions	X	X					X	X	Perform according to RECIST v1.1 criterion, by the same method used at baseline, q 8 wk (± 7 days) for the first 6 mo after C1D1 and q 12 wk (± 7 days) thereafter until radiographic disease progression, death, or study completion, whichever occurs first. Perform as scheduled, even if study treatment is delayed or omitted.
ECG	X								Baseline: Predose (single). Perform additional evaluations in the setting of cardiac symptoms and/or at the discretion of the investigator. Perform locally.
Hematology*	X	X	X	X	X	X	X		≤ 3 days prior to start of each cycle, unless more frequent assessment is clinically indicated.

Procedure	Baseline	All Remaining Parts on Treatment (Cycle = 28 days)						Post Treatment Follow-Up		Instructions				
	Days Prior to C1D1	Cycle 1 (± 3 Days)		Cycle 2 (± 3 Days)		Cycle 3-n (± 3 Days)		Short-Term ^a (30 ± 7 Days)	Long-Term (Every 90 ± 7 Days)					
		Day		Day		Day								
		≤28	1	15	1	15	1							
Coagulation	X									Only collected at baseline, unless more frequent assessment is clinically indicated.				

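### QTc is summarised only as outlier categories, and the Phase 1a triplicate ECGs with matched plasma samples have no pre-specified analysis, so a modest QT effect could easily be missed

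*SAP*

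**What the plan says.** **SAP.** Section 6.8.6 holds the ECG outputs. Quantitative results, including QTcB and QTcF, "will be provided in patient listings for absolute and change from baseline". There are two kinds of aggregate output:
- a normal/abnormal table: "The summary by cycle will classify patients as having normal or abnormal";
- an outlier table: "In addition, summaries of outlying corrected QT (QTc) intervals (QTc, QTcB, and QTcF) will be provided", with these limits: "Outlying intervals include absolute values >450 for males, >470 for females, >480 and >500 msec, and change from baseline >30 and >60 msec".

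ECG-related adverse events are shown if appropriate. No primary heart-rate correction is named. Table JZFA.6.1 takes baseline as the last value before dosing and gives no rule for triplicates. SAP 6.9 covers noncompartmental parameters and dose proportionality, plus a general allowance for exploratory work. It does not mention QTc.

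**Protocol, Phase 1a (Table JZFA.2.1).** On Cycle 1 Day 1 sites are to "collect digital ECGs for QT analysis in triplicate at predose, 2 hrs postdose", with a 24 h reading if possible. Day 15 is triplicate and predose, and there the table adds: "A corresponding PK sample should be collected after the ECG reading". The Cycle 1 Day 1 plasma schedule also has predose, 2 h and 24 h times. ECGs from Cycle 2 on are single and predose. Day 15 has plasma samples from 1 to 8 h after dosing but no ECG with them. Some ECGs and plasma samples are optional.

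**Protocol, Phase 1b (Table JZFA.2.2).** One baseline ECG is scheduled. Others are done only for cardiac symptoms or at the investigator's discretion.

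**Numbers (Protocol 5.1.1).** There are 3 to about 6 patients per dose level, and up to 10 at the RP2D.

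**The concern.** The protocol collects data that could estimate a QT effect, but the SAP commits only to a tally. Dichotomising QTc change at 30 or 60 msec discards most of its information, and dose levels are small. Every ECG with a stated postdose time follows the first dose. Scheduled ECGs from Day 15 on are predose, so no scheduled reading falls at the steady-state peak.

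Phase 1a is also the only scheduled source of on-treatment ECGs before the RP2D is given to about 4 × 20 + 30 = 110 patients in Phase 1b. Protocol 3.2.2 lists decreased heart rate among the nonclinical findings. QT/RR^(1/2) and QT/RR^(1/3) move apart as RR changes, so the correction to be relied on should be fixed in advance.

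**Working it through.** The documents give no QTc sample size, SD, target effect or decision rule, so there is no QTc figure to reproduce.

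**1. Zero outliers.** The exact two-sided 95% upper limit for 0/n is 1 − 0.025^(1/n). As a check against Protocol Table JZFA.10.1, n = 20 gives 0.168 (table 0.17) and n = 30 gives 0.116 (table 0.12). For the dose-level sizes here:
- n = 3: 1 − 0.292 = 0.708, or 71%
- n = 6: 1 − 0.541 = 0.459, or 46%
- n = 10: 1 − 0.692 = 0.308, or 31%

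**2. Counting against averaging at one dose level.** All inputs are assumed: normal QTc change; SD 10, 15 or 20 msec; true mean effect at the sampled times 5, 10 or 20 msec. The count uses four on-treatment ECGs per patient (correlation 0.5) and the smallest critical count with one-sided error of at most 5% under no effect. The mean-change test uses a single time and asks whether the lower 90% CI bound exceeds 0.

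Example, n = 10, SD 15: the chance that a patient has any change >30 msec is 0.0714 with no effect and 0.2413 with a 10 msec effect. The critical count is 3 (error 0.029). P(X ≥ 3 | 10, 0.2413) = 45%.

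| n | SD | Count >30: 5 / 10 / 20 msec | Mean change: 5 / 10 / 20 msec |
|---|---|---|---|
| 6 | 10 | 12 / 36 / 94% | 28 / 68 / 99% |
| 6 | 15 | 4 / 15 / 70% | 17 / 41 / 87% |
| 6 | 20 | 5 / 15 / 55% | 13 / 28 / 68% |
| 10 | 10 | 19 / 52 / 99% | 43 / 90 / 100% |
| 10 | 15 | 15 / 45 / 96% | 25 / 62 / 99% |
| 10 | 20 | 11 / 30 / 84% | 18 / 43 / 90% |

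This favours the count: it gets four ECGs instead of one, and a reference rate that the SAP does not set. Without such a rate a tally is hard to read. At SD 15 and no effect, at least one >30 msec change still appears in 36% of groups of 6 and 52% of groups of 10.

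**3. Predose sampling.** If trough effect is 25 to 50% of peak effect (assumed), 20 msec at peak is 5 to 10 msec predose. At n = 10, SD 15, detection by counting falls from 96% to 15–45%.

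**4. Pooled concentration-QTc model (simulation).** Assumed inputs:
- the seven example levels of Protocol Table JZFA.7.1, 6 patients each (42);
- two on-treatment pairs per patient (2 h after the first dose, Day 15 predose);
- SDs of change 6 (between) and 8 (within) msec, so √(36 + 64) = 10 in total;
- concentration CV 50%; steady-state peak 1.5 times the first-dose 2 h level; trough half the steady-state peak;
- RP2D at the 30 mg example level, for illustration only; true effect there 10 msec at the peak, hence 10/1.5 = 6.7 msec at 2 h and 5 msec at trough.

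Power of the slope test, adjusted for time, one-sided 5%:

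| Setting | Power |
|---|---|
| As above | about 90% |
| SDs 8/10 | 75% |
| No 2 h ECG | 69% |
| 3 patients per level | 68% |
| No level above the RP2D | 57% |
| No level above the RP2D and 3 per level | about 37% |

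In the first setting, any >30 msec outlier appears in about 15% of trials at the RP2D level and 52% across all levels. The 90% CI half-width at the RP2D peak is about 4 to 5 msec. The mean of one six-patient level gives 2.015 × 10/√6 = 8.2 msec.

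**The case against.** **The SAP does more than count.** This is true: it lists every absolute value and change, and classifies ECGs as normal or abnormal. Protocol 10.3.2 adds treatment-emergent ECG changes. None of these gives an estimate with an interval.

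**The paired data are not abandoned.** A reader might infer that they go unused. The documents do not say so: Protocol 10.1 foresees evaluating exposure against toxicity, with modelling if data warrant, and SAP 6.9 leaves exploratory work open. What stands is that no QTc analysis is pre-specified.

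**Detection may be adequate.** A reader might infer that any real QT effect would probably be missed. That depends on effect size, SD, peak-to-trough ratio and numbers, which the documents do not give. A sampled 20 msec effect shows in 55–99% of the settings in step 2.

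**The model's advantage is conditional.** Setting its 90% against the 15% chance of an outlier at the RP2D level compares 42 patients with 6. Across all levels the outlier figure is 52%, although that is the chance of any outlier and not an error-controlled test. Power falls without a level above the RP2D or without the 2 h ECG. The mandatory/optional marks cannot be placed reliably in the available text, so it is unclear whether the 2 h ECG is mandatory.

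**The model does not observe the missing peak.** This stands in full. It predicts there under an assumed linear, undelayed relation.

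**Conclusion.** The concern holds for a modest effect. QTc is listed per patient and summarised only by outlier category, and the triplicate ECG and plasma pairs have no pre-specified analysis. At a dose level of 6 to 10 patients, counting detects a sampled 5 to 10 msec effect in 4 to 52% of cases under the assumed SDs, and an outlier-free level leaves an upper limit of 31 to 71%. Estimation does better in every row of step 2 for those effects, and pooling across doses does better still when the 2 h pairs are collected and a level above the RP2D exists.

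The exact limits rest on the documents' patient numbers alone. The power figures rest on assumed SDs, concentrations and effect sizes.

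A reader might also infer that the RP2D will be cleared for QT because no outliers were seen. The documents set no such rule: Protocol 10.3.2 bases the final RP2D on all DLTs, TEAEs, PK and PD data.

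**What to change.** In SAP 6.8.6 and 6.9, for Phase 1a:
- Average triplicates at each time, including baseline, and name QTcF as the primary correction.
- Report mean change from baseline in QTcF by dose level and time, with 90% CI.
- Add a linear mixed-effects model of change in QTcF on time-matched LY3405105 concentration, pooled over dose levels, with a random patient intercept, nominal time and centred baseline QTcF. Report the predicted change with 90% CI at the RP2D's geometric mean Day 15 Cmax.
- Plot the data to check linearity and delay, state how many pairs contribute, and label the prediction as extrapolation if that Cmax lies outside the concentrations paired with ECGs.
- Keep the outlier table as supportive.

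The cost is SAP wording and a small amount of programming, with no new ECG or blood draw. SAP version 2 is based on protocol amendment (b), so the same update can bring in the mandatory/optional ECG and plasma schedule of amendment (c). The remaining limits are that the steady-state peak is still not observed, and that precision depends on how many optional pairs are collected.

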6.9. Pharmacokinetic/Pharmacodynamic Analyses

Unless stated otherwise, the Lilly pharmacokineticist will be responsible for the PK/PD analyses.

Pharmacokinetic parameter estimates for LY3405105 will be calculated by standard noncompartmental methods of analysis.

The primary parameters for analysis will be maximum concentration (C_{max}) and area under the concentration-time curve ($AUC_{0-tlast}$, $AUC_{0-\infty}$). Other noncompartmental parameters, such as half-life ($t_{1/2}$), apparent clearance (CL/F), apparent volume of distribution (V/F), and renal clearance of LY3405105 may be reported. Additional exploratory analyses will be performed if warranted by data and other validated PK software programs (for example, NONMEM) may be used if appropriate. The version of any software used for the analysis will be documented and the program will meet the Lilly requirements of software validation.

Pharmacokinetic parameter estimates will be evaluated to delineate effects of dose proportionality. Log-transformed C_{max} and AUC estimates will be assessed to estimate ratios of geometric means and the corresponding 90% CIs.

6.10. Biomarker Analyses

Biomarkers related to treatment, immune response, mechanism of action, and/or cancer will be measured and analyzed. The association of biomarker and clinical outcomes will be assessed via single-marker and/or multi-marker analyses.

6.11. Protocol Violations

All significant protocol violations will be summarized by pre-determined categories (eg, inclusion/ exclusion criteria, noncompliance with protocol procedures, drug dosage/intervention, use of excluded treatments, informed consent/assent process, continuing after meeting withdrawal criteria, or other). These violations will include deviations which can be identified

programmatically and those which can only be identified by the clinical research associate (CRA) during monitoring.

6.12. Interim Analyses

Because this is a dose-finding study, data will be reviewed on a dose level-by-dose level basis during the dose escalation, until the MTDs are determined. The purpose of these dose level-by-dose level reviews is to evaluate the safety data at each dose level and determine if a DLT has been observed that would suggest MTD has been met or exceeded. The investigators and the Lilly study team will make the determination regarding dose escalation based upon their review of the safety and tolerability data (and PK/PD data were available) as described in the protocol.

[figure not shown]
For Phase 1a, after all patients who are deemed evaluable for the assessment of dose levels complete DLT evaluation period or MTD is determined, an interim analysis for safety and PK will be conducted.

For Phase 1b, a safety review will be performed after the first 20 patients across all cohorts are enrolled and treated for 1 cycle, and then every 6 months afterward. The purpose of this safety review is to evaluate the safety and tolerability for each expansion cohort and determine if a dose-limiting equivalent toxicity (DLET) has been observed. For the first 20 patients enrolled into Phase 1b, if in 7 patients or more DLETs are observed, accrual may be temporarily paused, and the available data from Phase 1a and Phase 1b will be analyzed to potentially modify the RP2D or the study. Considerations for stopping recruitment should be given after discussion with the investigator and the Sponsor.

Continuous monitoring for safety and efficacy will occur in Phase 1b and if aggregate data suggest that continued enrollment is unlikely to alter the outcome or present an unreasonable risk to patients, enrollment into any one or all Cohorts 1 through 5 may be stopped.

Bayesian Toxicity Monitoring Plan (U-Design [WWW], version 1.3): Assuming the maximum permissible probability of toxicity is 0.3, the probability threshold for declaring excessive toxicity is 0.7, we may stop the trial if the posterior probability $P(\theta > 0.3|n, x) \geq 0.7$, where θ is the true toxicity rate, n is the current number of patients, and x is the number of DLETs. A precalculated decision table by posterior probability of toxicity (assuming a beta(0.5, 0.5) prior) is shown in [Figure JZFA.6.1](#). From the precalculated table, if the number of patients with DLETs observed among 5, 10, 15, and 20 treated patients is greater or equal to 2 (40%), 4 (40%), 6 (40%), and 7 (35%), respectively, based on the totality of data, accrual may be paused and the available data from Phase 1a and Phase 1b will be analyzed to potentially modify the RP2D or the study.

Table TM: Decision Table by Posterior Probability of Toxicity

Notes:

1.red denotes the posterior probability of toxicity $Pr(\theta > \theta_{max} | Data)$ is larger than $\theta_T = 0.7$.

2.green on the opposite.

Figure JZFA.6.1. Bayesian toxicity monitoring decision table.

If it is deemed that enough data are obtained to assess the primary objective and the secondary objectives, a CSR might be created before the last patient visit. In this case, all data until the data-cutoff date will be used for the analysis of safety, efficacy, PK, and PD biomarkers. All data defined in the protocol will continue to be collected from patients on treatment after the data-cutoff date. These data may be reported separately and the analyses on all patients including these data may not be performed.

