7.1.2. Dose Expansion (Phase 1b)

After the monotherapy RP2D has been determined from Phase 1a, approximately 20 patients will be enrolled in each of Phase 1b Cohorts 1-4. In Cohort 5, approximately 30 patients will be enrolled. Patients will receive LY3405105 at the RP2D orally daily for a 28-day cycle.

Study treatment should be continued until evidence of disease progression or discontinuation criteria is met. Patients with documented progressive disease may be allowed to continue LY3405105 if the patient is tolerating treatment and, in the opinion of the investigator, is deriving clinical benefit from continuing study treatment and continuation of treatment is approved by the Sponsor.

If DLT-equivalent toxicities occur in 33% or more of patients within a tumor-specific cohort expansion, then investigators and the Lilly CRP/CRS will assess the nature and severity of these toxicities. If a treatment-related death or Grade 4 toxicity not clearly due to underlying disease or extraneous occur, then the investigators and the Lilly CRP/CRS will assess the nature and severity of the toxicities and whether the trial should be stopped due to unacceptable toxicity. No additional patients will be accrued until this safety review is completed and a decision is made either to continue at the current dose or to de-escalate the dose and define a new dose for the expansion phase. The safety review and decision will be documented in writing.

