10.3.3.6. Biomarker Analyses

Biomarkers related to treatment, immune response, mechanism of action, and/or cancer will be measured and analyzed. The association of biomarker and clinical outcome will be assessed via single-marker and/or multi-marker analysis.

10.3.4. *Interim Analyses*

Because this is a dose-finding study, data will be reviewed on a dose level-by-dose level basis during the dose escalation, until the MTDs are determined. The purpose of these dose level-by-dose level reviews is to evaluate the safety data at each dose level and determine if a DLT has been observed that would suggest MTD has been met or exceeded. The investigators and the Lilly study team will make the determination regarding dose escalation based upon their review of the safety and tolerability data (and PK/PD data were available) as described in this protocol.

For Phase 1a, after all patients who are deemed evaluable for the assessment of dose levels complete DLT evaluation period or MTD is determined, an interim analysis for safety and PK will be conducted.

For Phase 1b, a safety review will be performed after the first 20 patients across all cohorts are enrolled and treated for 1 cycle, and then every 6 months afterward. The purpose of this safety review is to evaluate the safety and tolerability for each expansion cohort and determine if a dose-limiting equivalent toxicity (DLET) has been observed. For the first 20 patients enrolled into Phase 1b, if in 7 patients or more DLETs are observed, accrual may be temporarily paused, and the available data from Phase 1a and Phase 1b will be analyzed to potentially modify the RP2D, or the study. Considerations for stopping recruitment should be given after discussion with the investigator and the Sponsor.

Continued monitoring for safety and efficacy will occur in Phase 1b and if aggregate data suggest that continued enrollment is unlikely to alter the outcome or present an unreasonable risk to patients, enrollment into any one or all Cohorts 1-5 may be stopped.

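### SAP 6.12: the pause count of 7 in 20 does not follow from the stated posterior rule, which gives 0.6955 against a threshold of 0.7

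*SAP*

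**What the plan says.** The Bayesian Toxicity Monitoring Plan in SAP 6.12 sets the maximum permissible toxicity probability at 0.3. It continues: "the probability threshold for declaring excessive toxicity is 0.7, we may stop the trial if the posterior probability" that the true rate exceeds 0.3, given the data, is at or above 0.7. The prior is stated with the table: "A precalculated decision table by posterior probability of toxicity (assuming a beta(0.5, 0.5) prior"). The SAP then reads the pause counts off that table: the number of patients with DLETs "among 5, 10, 15, and 20 treated patients is greater or equal to 2 (40%), 4 (40%), 6 (40%), and 7 (35%), respectively". The note under Figure JZFA.6.1 ("red denotes the posterior probability of toxicity") colours a cell when the posterior is strictly greater than 0.7, whereas the text allows equality.

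The 20-patient count also appears without a derivation earlier in SAP 6.12 ("if in 7 patients or more DLETs are observed, accrual may be temporarily paused") and in Protocol 10.3.4 ("For the first 20 patients enrolled into Phase 1b, if in 7 patients or more DLETs are observed, accrual may be temporarily paused").

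**The concern.** The SAP gives everything needed to derive the counts (toxicity limit, threshold, prior) and says the counts come from that calculation. One of the four does not. It is the one at 20 patients, the sample size at which both documents schedule the first Phase 1b safety review. If exactly 7 of the first 20 patients have a DLET, the printed count is met and the stated posterior criterion is not.

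The mismatch may also reach beyond that cell. If the table was built with a different prior from the one printed, the smallest qualifying counts at some other sample sizes differ from those the text implies. The rule is written for the current number of patients, and SAP 6.12 adds that "Continuous monitoring for safety and efficacy will occur in Phase 1b", so intermediate rows could be consulted.

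**Working it through.** **Inputs, all from SAP 6.12.** Toxicity limit 0.3; posterior threshold 0.7; prior Beta(0.5, 0.5); stated counts 2, 4, 6 and 7 at n = 5, 10, 15 and 20.

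**Formula.** With x patients with DLETs among n, the posterior for the toxicity rate θ is Beta(0.5 + x, 0.5 + n − x). The pause count is the smallest x for which P(θ > 0.3) is at least 0.7. At 7 of 20 the posterior is Beta(7.5, 13.5).

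**Reproducing the SAP's counts**

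| n | Stated count | Posterior one below | Posterior at stated count | Meets 0.7? |
|---|---|---|---|---|
| 5 | 2 | 0.337 | 0.703 | yes |
| 10 | 4 | 0.519 | 0.762 | yes |
| 15 | 6 | 0.624 | 0.804 | yes |
| 20 | 7 | 0.513 | 0.6955 | no |

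At 8 of 20 the posterior is 0.836. The rule as written therefore gives 2, 4, 6 and 8. Numerical integration of the 7-of-20 posterior gives 0.695548, so the shortfall is 0.7 − 0.6955 = 0.0045. The result is the same whether the comparison is strict or allows equality.

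**Possible explanations**

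- *Another prior.* Under Beta(1, 1) the posteriors at the four stated counts are 0.744, 0.790, 0.825 and 0.723, and all four are the smallest qualifying counts.
- *Rounding.* 0.6955 rounds to 0.70. That would satisfy the text, which allows equality, but not the figure note, which requires more than 0.7.

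**Telling them apart.** For n up to 20 the two priors give different smallest counts only at n = 8, 11, 14, 17 and 20:

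| Cell | Beta(0.5, 0.5) | Beta(1, 1) | Smallest count, Beta(0.5, 0.5) vs Beta(1, 1) |
|---|---|---|---|
| 3 of 8 | 0.692 | 0.730 | 4 vs 3 |
| 4 of 11 | 0.689 | 0.724 | 5 vs 4 |
| 5 of 14 | 0.690 | 0.722 | 6 vs 5 |
| 6 of 17 | 0.692 | 0.722 | 7 vs 6 |
| 7 of 20 | 0.6955 | 0.723 | 8 vs 7 |

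In this range 7 of 20 is the only cell under Beta(0.5, 0.5) that lies below 0.7 yet rounds to 0.70. If the sponsor's table flags 3 of 8, 4 of 11, 5 of 14 and 6 of 17, two-decimal rounding is not the explanation and those cells fit Beta(1, 1). If it flags only 7 of 20 among the five, rounding is the likely cause.

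**Size.** The chance of reaching the count is binomial for a single look at n = 20. For looks at 5, 10, 15 and 20 it is an exact recursion with counts 2/4/6/7 or 2/4/6/8.

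| True DLET rate | Single look: 7+ vs 8+ | Gap = P(exactly 7 of 20) | Four looks: last count 7 vs 8 |
|---|---|---|---|
| 0.20 | 8.7% vs 3.2% | 5.5 points | 31.3% vs 29.9% |
| 0.30 | 39.2% vs 22.8% | 16.4 points | 62.0% vs 57.9% |
| 0.35 | 58.3% vs 39.9% | 18.4 points (maximum) | 75.7% vs 71.1% |
| 0.40 | 75.0% vs 58.4% | 16.6 points | 86.3% vs 82.1% |

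These are chances of reaching a discretionary count, not of an automatic pause.

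**The case against.** The strongest reply is that nobody running the trial faces two competing counts. Seven of 20 is printed in Protocol 10.3.4 and twice in SAP 6.12, and the protocol's version does not rest on the posterior rule. The shortfall is 0.0045, the printed count is the more cautious one, and every pause is permissive and subject to the totality of data. Protocol 7.1.2 also has its own review trigger: "If DLT-equivalent toxicities occur in 33% or more of patients within a tumor-specific cohort expansion". A team that follows the printed count misses no review because of this mismatch. If all four listed looks are used, the two versions differ by at most 4.6 points at the rates computed. The concern about other sample sizes depends on a table that is not visible here and on a prior misprint that is not proven.

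Most of this stands, and it limits the weight of the point. The difference between the strict and non-strict threshold also changes no decision at exact precision. What the reply does not remove is the SAP's explicit statement that 7 of 20 comes from the posterior table. Under the stated inputs it does not. The single-look comparison is also relevant, because both documents schedule a review at 20 patients.

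**Conclusion.** The point holds. Under the prior, limit and threshold printed in SAP 6.12, the counts are 2, 4, 6 and 8, not 2, 4, 6 and 7. The disagreement is confined to exactly 7 DLETs in 20 patients if the printed prior is right, and could extend to n = 8, 11, 14 and 17 if it is not. It should be fixed, though its practical effect is limited: a prespecified safety count does not follow from its stated derivation, but following the printed count errs towards caution.

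The conclusion rests on the SAP's text alone; the cells of Figure JZFA.6.1 could not be checked. Both explanations, a Beta(1, 1) prior and rounding, are conjecture. The probabilities assume independent patients with a common DLET rate.

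**What to change.** Check the whole of Figure JZFA.6.1 against the prior actually used to build it, starting with the cells 3 of 8, 4 of 11, 5 of 14, 6 of 17 and 7 of 20. Then make the prior, the threshold (including whether equality counts) and the 20-patient count agree across both statements in SAP 6.12, the figure with its note, and Protocol 10.3.4. Printing the attained posterior probability beside each listed count would be a useful addition. This review does not say which boundary is right.

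The cost is a clarification in SAP 6.12 and a check of one table. Protocol 10.3.4 changes only if the reconciliation changes the count. No patients, procedures or delay are involved.
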